12.7 Extension Day 547 (± 3)

All risks and associated details regarding the EGD procedure will be discussed with the patient by the EGD provider.

- Patient should arrive fasting for the EGD procedure, as specified by instructions from the EGD provider.
- Collect AE, SAE, and changes in concomitant medications. Capture all concomitant medications provided to the subject during the EGD.
- Perform the EGD with biopsy following procedures provided by Allakos and all EGD facility SOPs.

12.8 Extension Day 561 (± 3) to Extension Day 701 (± 3)

The following procedures will be performed on Extension Days 561, 589, 617, 645, 673, and 701 (± 3 days).

The following procedures will be performed prior to study drug infusion:

- Have patient complete the SF-36 Health Survey.
- Determine body weight.
- Enter PID and weight into IRT.
- Document any changes in diet.
- Collect vital signs.
- Perform urine pregnancy test if patient is of childbearing potential.
- Perform symptom-directed physical examination, as needed.
- Collect blood samples for CBC and blood chemistry.
- The study pharmacist will prepare study drug at 3 mg/kg using the weight obtained at the visit.

Procedures associated with the infusion of study drug include:

- Premedication may be administered at the Investigator's discretion, in discussion with the Medical Monitor.
- Infuse 100 mL of study drug using an infusion pump over at least 1 to 4 hours, depending on the Investigator's discretion and tolerance to prior infusions. See Pharmacy Manual for Infusion Rates. Record the start and stop times of the infusion including any times the infusion is interrupted.

- Collect vital signs 15 (± 5) minutes after the start of infusion.
- An unscheduled ADA blood sample may be obtained if an immunogenicity-related AE is suspected.

The following procedures will be performed after study drug infusion:

- Collect vital signs immediately following (+5 minutes) the end of infusion.
- Collect CBC with differential 1 hour (± 15 minutes) after the end of infusion.
- Observe the patient for at least 1 hour after the end of infusion.

Concomitant medication use and AE (including AESI and SAE) will be documented throughout the clinic visit.

12.9 Extension Day 701 + 28 (± 3) days *Only if Previous Doses were Missed*

The following procedures will be performed on all Infusion Days after Day 701 – *only* relevant if previous doses were missed – until a total of 26 doses have been received.

The following procedures will be performed prior to study drug infusion:

- Have patient complete the SF-36 Health Survey.
- Determine body weight.
- Enter PID and weight into IRT.
- Document any changes in diet.
- Collect vital signs.
- Perform urine pregnancy test if patient is of childbearing potential.
- Perform symptom-directed physical examination, as needed.
- Collect blood samples for CBC and blood chemistry.
- The study pharmacist will prepare study drug at 3 mg/kg using the weight obtained at the visit.
- Procedures associated with the infusion of study drug include:
- Premedication may be administered at the Investigator's discretion, in discussion with the Medical Monitor.

- Infuse 100 mL of study drug using an infusion pump over at least 1 to 4 hours, depending on the Investigator's discretion and tolerance to prior infusions. See Pharmacy Manual for Infusion Rates. Record the start and stop times of the infusion including any times the infusion is interrupted.
- Collect vital signs 15 (± 5) minutes after the start of infusion.
- An unscheduled ADA blood sample may be obtained if an immunogenicity-related AE is suspected.

The following procedures will be performed after study drug infusion:

- Collect vital signs immediately following (+5 minutes) the end of infusion.
- Collect CBC with differential 1 hour (± 15 minutes) after the end of infusion.
- Observe the patient for at least 1 hour after the end of infusion.

Concomitant medication use and AE (including AESI and SAE) will be documented throughout the clinic visit.

12.10 Follow-up Extension Day 729 (± 3) or 28 (± 3) Days after Last Dose, if ET or if Missed Doses are being made up

All risks and associated details regarding the EGD procedure will be discussed with the patient by the EGD provider.

- Patient should arrive fasting for the EGD procedure, as specified by instructions from the EGD provider.
- Collect AE, SAE, and changes in concomitant medications. Capture all concomitant medications provided to the patient during the EGD.
- Perform the EGD with biopsy following procedures provided by Allakos and all EGD facility SOPs.

For Early Termination: Perform EGD 28 (± 3) days after the last dose of study drug or prior to this, if necessary, to ensure compliance with the visit. If patient discontinues the study more than 28 days after the last dose of study drug, perform the EGD as soon as possible.

12.11 Follow-up Extension Day 736 (± 3) or 35 (± 3) Days after Last Dose, if ET or if Missed Doses are being made up

Procedures for Extension Day 736 or 35 (± 3) days after last dose of study drug, include:

- Determine body weight.
- Collect vital signs.
- Have patient complete the SF-36 Health Survey.
- Document any changes in diet.
- Perform symptom-directed physical examination, as needed.
- Collect blood samples for CBC, blood chemistry, PK, and ADA.
- Collect urine for urinalysis and perform urine pregnancy test if patient is of childbearing potential.
- Instruct patient to continue completing daily ePRO questionnaire through 84 days after the last dose of study drug.

Concomitant medication use, AESI, and SAE will be documented throughout the clinic visit.

12.12 Follow-up Extension Day 757 (± 3) and Day 785 (± 3) or 56 and 84 (± 3) Days after Last Dose, if ET or if Missed Doses are being made up

Procedures for Extension Day 757 and Day 785 or 56 (± 3) days and 84 (± 3) days after the last dose of study drug, include:

- Have patient complete the SF-36 Health Survey.
- Document any changes in diet.
- Collect blood sample for CBC.
- Instruct patient to continue completing daily ePRO questionnaire through 84 days after the last dose of study drug.

Concomitant medication use, AESI, and SAE, will be documented throughout the clinic visit.

13. Adverse Event Reporting and Documentation

13.1 Adverse Events

In accordance with 21 Code of Federal Regulation (CFR) 312.32(b) and International Conference on Harmonisation (ICH) Guidance E2A, an AE is any untoward medical occurrence in a clinical investigation of a patient administered a pharmaceutical product and that does not necessarily have a causal relationship with the treatment. An AE is therefore any unfavorable and unintended sign (including an abnormal laboratory finding), symptom, or disease temporally associated with the administration of an investigational product, whether or not related to that

investigational product. An unexpected AE is a type not identified in nature, severity, or frequency in the current Investigator's Brochure or of greater severity or frequency than expected based on the information in the Investigator's Brochure.

Examples of an AE include:

- Significant worsening or exacerbation of underlying medical condition.
- Significant abnormal findings from physical examinations, vital signs or laboratory tests.

The following examples are not considered AE:

- Medical or surgical procedure, although the condition leading to the procedure is usually an adverse event.
- Anticipated day-to-day fluctuations of preexisting medical conditions (including laboratory values) as long as worsening from baseline does not occur.
- Signs or symptoms of the disorder being studied, unless they become more severe or occur with a greater frequency than occurring at baseline.

All non-serious AE that are not AESI, whether elicited by questions from study staff, volunteered, or noted on physical examination/laboratory testing, and regardless of causality or severity, will be assessed and recorded in the eCRF beginning after first administration of study drug and ending at Extension Day 785 or 84 (± 3) days after last dose of study drug if patient is early terminating or if missed doses are being made up.

13.2 Serious Adverse Events

A serious adverse event is defined as an adverse event that meets that one of the following criteria:

- Death
- A life-threatening AE that places the patient at risk of death at the time of the event. It does not refer to an event that hypothetically might cause death if it were more severe.
- Inpatient hospitalization or prolongation of existing hospitalization.
- A persistent or significant disability/incapacity.
- A congenital anomaly/birth defect occurring in the offspring of a study patient.
- Other important medical events may also be considered a SAE when, based on appropriate medical judgment, they jeopardize the patient or require intervention to prevent one of the outcomes listed above.

Serious adverse events will be assessed and recorded after the first administration of study drug and ending at Extension Day 785 (± 3) or 84 (± 3) days after the last dose of study drug if patient is early terminating or if missed doses are being made up.

13.3 Adverse Events of Special Interest

Adverse events of special interest for this study include:

- Malignancies confirmed by histopathological report. (Mast cells and eosinophils are part of the normal immune response, by decreasing their function, AK002 could theoretically increase the risk of malignancy).
- Parasitic infections confirmed by positive clinical laboratory test. (Eosinophils are especially active in protecting the body from parasitic infections and decreasing their function could theoretically increase the risk of parasitic and opportunistic infections).
- Opportunistic infections (infections known to be more severe or occur more frequently in immunosuppressed populations) as confirmed by positive clinical laboratory test.
- Infusion-related reactions and hypersensitivity reactions, including anaphylaxis.

Beginning from the time of first study drug infusion and ending at Extension Day 785 (± 3) or 84 (± 3) days after the last dose of study drug if the patient is early terminating or if missed doses are being made up, any new AESI must be recorded in the Adverse Event eCRF and designated as an “adverse event of special interest.” If new information related to any previously reported AESI is identified, the appropriate eCRF should be updated.

13.4 Infusion-Related Reactions

All AE, considered by the Investigator to be related to the infusion of the biological substance and occurring within 24 hours of the start of the study drug infusion, should be captured as 1 IRR.

Common symptoms of IRR include:

- Flushing
- Chills
- Back or abdominal pain
- Chest discomfort or tightness
- Dizziness
- Shortness of breath
- Headache

- Hypotension or hypertension
- Nausea
- Vomiting
- Sweating
- Fever
- Urticaria
- Pruritus
- Bronchospasm

All symptoms experienced by a patient during an infusion-related reaction will be listed in the eCRF under 1 infusion-related reaction, unless the Investigator believes a symptom is not part of the infusion-related reaction, in which case it will be recorded separately. The start time of the infusion-related reaction will be captured as the start time of the first symptom and the end time of the infusion-related reaction will be captured as the end time of the last symptom.

13.5 Anaphylaxis

A suspicion of anaphylaxis will be carefully monitored and treated according to standard of care. Emergency crash cart equipment and medications, including multiple doses of epinephrine, vasopressors, and bronchodilators, will be available at all times during the conduct of the study. To define anaphylactic reactions in a consistent and objective manner, all AE of suspected anaphylaxis will be evaluated using Sampson's Criteria for Anaphylaxis ([Appendix 19.4](#)). The assessment of an adverse event will be done pursuant to definitions set forth by ICH Good Clinical Practice (GCP) guidelines and applicable regulatory requirements.

If a patient experiences signs or symptoms of anaphylaxis, the patient may be treated with standard of care, such as diphenhydramine, acetaminophen, methylprednisolone, epinephrine, and other supportive measures along with cessation of the infusion.

13.6 Evaluating Adverse Events and Serious Adverse Events

13.6.1 Establishing Diagnosis

Whenever possible, diagnoses should be given when signs and symptoms are due to a common etiology (e.g., dysuria, urinary nitrites should be reported as a urinary tract infection). If the diagnosis is not known, individual signs and symptoms should be assessed and recorded in the Adverse Event eCRF as separate AE. The Investigator (or qualified Subinvestigator) must assign the AE attributes listed in the following sections and is responsible for ensuring their capture in the source documentation.

13.6.2 Assessment of Intensity

The Investigator will use their clinical judgment as well as the guidelines laid out in the National Cancer Institute Common Terminology Criteria for Adverse Events (CTCAE) Version 5.0 (or most current version) tables (Table 2 and [Appendix 19.3](#)) to assess the intensity of each AE and SAE.

Table 2 Adverse Event Severity per the National Cancer Institute Common Terminology Criteria for Adverse Events Version 5.0

Grade*	Description
1	Mild; asymptomatic or mild symptoms; clinical or diagnostic observations only; intervention not indicated
2	Moderate; minimal, local or noninvasive intervention indicated; limiting age appropriate instrumental activities of daily living
3	Severe or medically significant but not immediately life-threatening, hospitalization or prolongation of hospitalization indicated; disabling; limiting self-care activities of daily living
4	Life-threatening consequences, urgent intervention indicated
5	Death related to adverse event

*Grade refers to the severity of the adverse event. The CTCAE displays Grades 1 to 5 with unique clinical descriptions of severity for each AE based on this general guideline.

The term “severe” is a measure of intensity, and a severe AE is not necessarily a SAE. When the intensity of an AE changes more than once a day, the maximum severity for the event should be entered into the Adverse Event eCRF. If the intensity changes over a number of days, these changes should be recorded separately (i.e., as having distinct onset dates).

13.6.3 Assessment of Causality to Study Drug

The Investigator should use clinical judgment, as well as the guidelines in [Table 3](#), to assess the relationship between study drug and AE.

Table 3 Adverse Event Relationship to Study Drug

Relationship to Study Drug	Comment
Related	There is clear evidence that the event is related to the use of study drug (e.g., confirmation by positive rechallenge test, if possible). Another etiology is considerably less likely.
Possible	The event cannot be explained by the patient's medical condition, concomitant therapy, or other causes, and there is a plausible temporal relationship between the event and study drug administration.
Unlikely/Remote	An event for which an alternative explanation is more likely (e.g., concomitant medications or ongoing medical conditions) or the temporal relationship to study drug administration and/or exposure suggests that a causal relationship is unlikely. (For reporting purposes, Unlikely/Remote will be grouped together with Not Related.)
Not Related	The event can be readily explained by the patient's underlying medical condition, concomitant therapy, or other causes, and therefore, the Investigator believes no relationship exists between the event and study drug.

13.6.4 Assessment of Causality to Study Procedure

The Investigator should use clinical judgment as well as the guidelines in Table 4 to assess the relationship between study procedure and AE. Assessment of causality to Study Procedure should include causality to such items as EGD with biopsy or blood draw (as appropriate), or other. Infusion-related reactions should not be assessed in relation to Study Procedure, only in relation to Study Drug.

Table 4 Adverse Event Relationship to Study Procedure

Relationship to Study Procedure	Comment
Related	There is clear evidence that the event is related to a study procedure.
Possible	The event cannot be explained by the patient's medical condition, concomitant therapy, or other causes, and there is a plausible temporal relationship between the event and a study procedure.
Unlikely/Remote	An event for which an alternative explanation is more likely (e.g., concomitant medications or ongoing medical conditions) or the temporal relationship to any study procedure suggests that a causal relationship is unlikely. (For reporting purposes, Unlikely/Remote will be grouped together with Not Related.)
Not Related	The event can be readily explained by the patient's underlying medical condition, concomitant therapy, or other causes, and therefore, the Investigator believes no relationship exists between the event and a study procedure.

13.6.5 Action Taken

Action taken with respect to study drug will be categorized as none, study drug permanently discontinued (infusion is interrupted and is not restarted, and no subsequent infusions are given), study drug temporarily withdrawn (infusion is interrupted and is restarted, or the next infusion is still administered as planned), or other (specify).

Action taken with respect to study participation will be categorized as none, withdrawal from study participation, or other (specify).

Action taken with respect to treatment of an AE will be categorized as none, concomitant medication, concomitant procedure, or other (specify).

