Study Design cont.	
 • An EGD with biopsy will occur on Day 211 (± 3), Day 547 (± 3), and Day 729 (± 3) or 28 (± 3) days after last dose of study drug if early termination (ET) or if patient received additional missed doses. • Patients will be followed for 84 days after the last dose. Follow-up will occur on Extension Day 736 (± 3), Day 757 (± 3), and Day 785 (± 3) or 35, 56, and 84 (± 3) days after last dose of study drug if ET or if patient received additional missed doses. 
The extension study does not include fasting requirements. Patients underwent a standardized baseline evaluation of eating habits, food habits/restrictions, and food avoidance behaviors during Study AK002-003 and will be asked at study visits whether any changes have been made from the baseline diet.
 
Total duration of Study AK002-003X will be approximately 28 months if doses are administered monthly and none are missed, or longer, as needed for the patient to receive all 26 doses.

Objective	
The objective of the study is to generate open-label, longer-term safety, tolerability, and efficacy follow-up data in patients with EG and/or EoD who completed Study AK002-003 or were discontinued from treatment due to high eosinophil counts prior to infusions 2, 3, or 4.
 
The objective of this extension study is also to give patients that received placebo in Study AK002-003 access to AK002.

Safety Endpoints	
The safety and tolerability of AK002 will be assessed by determining the incidence, relationship to study drug, and severity of TEAE, withdrawals due to AE, vital signs, laboratory tests, changes in concomitant medication use due to AE, immunogenicity, and other safety parameters.

Pharmacodynamic/ Efficacy Endpoints	
 • Short-Form 36 Health Survey (SF-36) questionnaire • Gastrointestinal symptomatology (PRO questionnaire) • Change in blood eosinophil count • Change in eosinophil counts in gastric and/or duodenal biopsies
Study Population	
Patients who complete Study AK002-003 or were discontinued from treatment due to high eosinophil counts prior to infusions 2, 3, or 4 will have the option to receive AK002 in an open-label manner.
 
A patient was categorized as having completed Study AK002-003 if 4 infusions of study drug were administered and the patient was followed through Day 113 (± 3) of Study AK002-003.

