13.9 Study Withdrawal Criteria

Patients will be discontinued from the study in the event that:

- Occurrence of an exclusion criterion, which is clinically relevant and affects the patient's safety, if discontinuation is considered necessary by the Investigator and/or Sponsor.
- Rebounding of eosinophil counts to $>1500/\mu\text{L}$ in patients who entered the study with eosinophil levels $>1500/\mu\text{L}$, had an IRR during the first and/or second infusions, and whose eosinophil counts were initially suppressed after study drug will be withdrawn from the study.
- Serum transaminases (alanine aminotransferase and/or aspartate aminotransferase) $>3 \times$ upper limit of normal (ULN) and total bilirubin $>2 \times$ ULN (confirmed by subsequent repeat) without an alternative explanation.
- Elevation of alanine aminotransferase or aspartate aminotransferase $>3 \times$ ULN (confirmed by repeat) with the appearance or worsening of symptoms felt by the Investigator to be potentially related to hepatic inflammation, such as fatigue, nausea, vomiting, right upper quadrant pain or tenderness, fever, and rash.

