15.5 Analysis of Safety Endpoints

Adverse Events: All AE will be coded using the Medical Dictionary for Regulatory Activities (MedDRA) and will be classified by MedDRA system organ class and preferred term. Listings will include all AE collected on study. The summaries of AE will be based on TEAE, defined as an AE reported in the clinical database with a date of onset (or worsening) on or after the start date of the first intravenous infusion of the study medication.

Patient incidence (N and %) of TEAEs will be summarized as follows:

- Overview of TEAE to include
 - Number (%) of patients who report at least 1 TEAE overall, by severity and by relationship
 - Number (%) of patients who report at least 1 serious TEAE
 - Number (%) of patients who report at least 1 TEAE leading to treatment discontinuation
 - Number (%) of patients who report at least 1 TEAE of special interest
- TEAE by preferred term
- TEAE by system organ class and preferred term
- TEAE by maximum severity, system organ class, and preferred term
- Drug-related TEAE by system organ class and preferred term
- TEAE leading to withdrawal by system organ class and preferred term
- Serious TEAE by system organ class and preferred term
- TEAE of special interest by system organ class and preferred term

Clinical Laboratory Assessments: Samples will be obtained for the clinical laboratory tests identified in Section 11.4, and laboratory tests to be summarized include blood chemistry, hematology, urinalysis, and ADA.

Descriptive statistics will be used to summarize laboratory results at baseline, each visit, and the change from baseline for each visit. In addition, shift tables will summarize the laboratory results relative to normal reference ranges at baseline and each post-baseline time point.

Vital Signs: Vital signs will be summarized at baseline, each visit, and change from baseline at each visit.

Physical Examination: New or worsening symptoms in the symptom-directed physical examinations will be included in the by-patient data listings.

Concomitant Medications: All medications will be coded using the most current World Health Organization Drug Dictionary. Concomitant medications will be summarized by Anatomical Therapeutic Chemical Class and preferred term.

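### The Section 13.6.5 definition of permanent discontinuation omits an adverse event that ends dosing outside an infusion in a patient who stays on study, so the Section 15.5 treatment-discontinuation count could miss it

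*Combined protocol and SAP*

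**What the plan says.** Section 13.6.5 of the protocol records the action taken on study drug in four categories: none, permanently discontinued, temporarily withdrawn and other. The second is defined as "study drug permanently discontinued (infusion is interrupted and is not restarted, and no subsequent infusions are given". The last two read "study drug temporarily withdrawn (infusion is interrupted and is restarted, or the next infusion is still administered as planned), or other (specify".

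A separate field in the same section covers participation: "Action taken with respect to study participation will be categorized as none, withdrawal from study participation, or other (specify".

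Section 14.2 allows study treatment to be stopped at any time, lists an AE as one reason, and sets no condition that an infusion be under way. It also encourages patients who stop drug to stay on study and complete assessments.

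Section 15.5 plans an overview line, "Number (%) of patients who report at least 1 TEAE leading to treatment discontinuation", and a separate table of treatment-emergent AEs (TEAEs) that led to withdrawal. It does not say which recorded field supplies either. The safety endpoints in the synopsis include "withdrawals due to AE".

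**The concern.** The definition of permanent discontinuation joins two conditions: an infusion was broken off, and dosing then ended. Dosing is every 28 days, so an AE may well be found, or a decision to stop be taken, when no infusion is running. Such a patient meets the second condition but not the first. If the patient then follows the advice in Section 14.2 and stays on study, no named category in either field records that the AE ended treatment.

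What is at stake is the accuracy of one safety count. Long-term safety and tolerability are a main aim of this extension, and AEs that come to light between infusions are part of what it is meant to describe. A count that leaves some of them out makes the drug look better tolerated than the data show.

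**Working it through.** No published figure needs reproducing. The check sets the sections side by side.

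**1. What the category requires.** Let A mean that an infusion was interrupted and not restarted, and B that no later infusions are given. Permanent discontinuation needs A and B. Temporary withdrawal needs either an interrupted and restarted infusion or a next infusion given as planned. A patient with B but not A meets neither definition, because there is no next infusion. *None* would be untrue. That leaves *other*.

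**2. Whether B without A is a case the protocol expects.** It is.
- Section 14.2 puts no infusion condition on stopping treatment for an AE.
- Section 13.3 lists four groups of AEs of special interest. Three of them (malignancies, parasitic infections, opportunistic infections) need histopathology or laboratory confirmation, so they are unlikely to be established during an infusion.
- Table 1, note 17, has chemistry drawn before each infusion, so an abnormal result need not coincide with an interrupted one.
- Section 13.4 counts infusion-related reactions up to 24 hours from the start of infusion. Section 9.6 requires the infusion to be complete within 8 hours of preparation. So at least 24 − 8 = 16 hours of that window fall after the infusion has ended. A reaction starting then and ending dosing also fails A. This shows that the case can arise, not how often.

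**3. How each case is coded and where it can be counted.** The last two columns assume that the treatment-discontinuation line uses the study-drug field and the withdrawal table uses the participation field. The documents do not state this.

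| Case | Study-drug field | Participation field | Treatment-discontinuation line | Withdrawal table |
|---|---|---|---|---|
| (a) AE breaks off an infusion, dosing ends, patient stays on study | permanently discontinued | none | counted | not counted |
| (b) AE ends dosing between infusions or after one is complete, patient stays on study | other | none | **missed** | not counted |
| (c) Section 13.9 criterion met between infusions | other | withdrawal | **missed** | counted |
| (d) AE causes a dose to be skipped, dosing resumes | other (nothing else clearly fits) | none | rightly not counted | rightly not counted |

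Cases (a) and (b) have the same effect on treatment but are counted differently. Case (c) is counted once, so the two Section 15.5 outputs could disagree about the same patient.

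**4. Size.** The documents give no rate for case (b). Section 15.1 plans about 60 patients, and Section 15.2 analyses safety in all who are dosed. Each patient missed lowers the overview percentage by 1/60 = 1.7 percentage points; two would lower it by 2/60 = 3.3 points.

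**The case against.** Several points on the other side are sound.

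- **The participation field has no infusion condition.** A reader might infer that all the liver and eosinophil criteria in Section 13.9 escape the AE counts. The documents do not support that. Section 13.9 opens "Patients will be discontinued from the study in the event that", so these patients fit the withdrawal category, and Section 15.5 has a table to match. All that remains is that their study-drug field would literally still read *other*.
- **No source field is named.** Section 15 leaves full data handling to a separate Statistical Analysis Plan, which is not in the text reviewed here. It may use another field or rule. This stands, and it makes the undercount conditional.
- **No data are lost.** The free-text entry keeps the information, and many investigators would tick permanent discontinuation whatever the parenthesis says. This also stands, but coding would then depend on how literally each site reads the definition.
- **Disposition may help.** Under Section 14.1 a patient who stops early is not a completer. But Section 15.4 summarises reasons for leaving the study only, and does not say how it treats a patient who stops drug and finishes follow-up.
- **The wording on temporary withdrawal is loose.** Its second limb can be read without any interruption. That reading does not help case (b), where no next infusion is given.
- **Skipped doses are a different matter.** A reader might count AE-driven skips as missed discontinuations. Section 9.4 lets a skipped dose be made up later, so it does not belong in that count. The gap there is only a missing category.

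**Conclusion.** The point holds for one case: an AE ends dosing while no infusion is in progress and the patient stays on study. The protocol expects this case, and its own definition misclassifies it. Confidence is high for the gap in the definition and moderate for any effect on the count. That effect assumes that sites code literally, that the overview line comes from the coded category, and that *other* entries are not reviewed. On those assumptions each such patient costs 1.7 percentage points.

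Two stronger conclusions should be avoided. A reader might infer that the AE-discontinuation counts are confined to reactions during infusion; the participation field and the withdrawal table rule that out. A reader might also try to size the problem by the share of calendar time spent infusing. That is a share of time and not of events, and Section 2.3 reports infusion-related reactions as the most common TEAEs, so events are not spread evenly over time.

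**What to change.** Change data definitions only; clinical management is not affected.

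1. In Section 13.6.5, define permanent discontinuation as no further study drug given because of the AE, whether or not an infusion was in progress.
2. In Section 15.5 and the Statistical Analysis Plan, state that this category drives the treatment-discontinuation line and that the participation field drives the withdrawal table.
3. Before database lock, review all *other* entries in the study-drug field and recode those that meet the new definition.
4. Optionally, add a category for a dose skipped or delayed because of an AE, reported separately from discontinuations.

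The cost is minor wording and eCRF guideline work, plus a review of free-text entries for about 60 patients. No new data are needed. The reported number of AE discontinuations may rise.
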